2.4.4.1 Sensitivity analysis

To account for the impact of protocol deviations on the primary endpoint, sensitivity analyses will be performed. The primary analysis specified in [Section 2.4.3](#) will be repeated using the PP population using OC.

2.4.4.2 Subgroup analysis

Additionally, to evaluate the consistency of the results of the primary analysis across different subgroups of interest, the primary analysis specified above ([Section 2.4.3](#)) will be repeated based on the ITT population and using the ‘No Change’ imputation method, stratifying for each of the following subgroups specified below:

- Gender (Male, Female)

- Baseline Severity score of the ILA at maximum frown (Grade 2 (Moderate), Grade 3 (Severe))
- Prior botulinum toxin use (Botox, Xeomin, Dysport, Jeaveau, Other)
- Fitzpatrick skin type (I-III, IV-VI)

The Breslow-Day test will not be used to assess the homogeneity of odds ratios across subgroup categories. For each subgroup, the responder rates, difference in responder rates between the treatment groups, and the corresponding 95% CI will be presented.

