5. SELECTION AND DISPOSITION OF CLINICAL STUDY POPULATION

5.1 Number of Subjects

As a screen failure rate of approximately 10% is anticipated, approximately 134 subjects will be screened in order to get 120 subjects enrolled in a 3:1 ratio to QM1114-DP 50 U (N=90) or placebo (N=30). It is expected that each center will recruit a similar number of subjects.

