5.2.1 Inclusion Criteria

1. Male or female, 18 years of age or older.
2. **CCI**
[REDACTED]
3. [REDACTED]
4. Previous repeated treatments with BoNT-A products for aesthetic use within 3 years prior to the screening visit.
5. Female of non-childbearing potential (i.e., post-menopausal [absence of menstrual bleeding for 1 year prior to screening, without any other medical reason], or has undergone hysterectomy or bilateral oophorectomy).

OR

Female of childbearing potential with a negative urine pregnancy test at screening and baseline, and agrees to use a highly effective and approved contraceptive method for the duration of the study. A highly effective method of contraception is defined as:

- Bilateral tubal ligation;
- Combined (estrogen and progesterone containing) oral, intravaginal or transdermal contraceptives that inhibit ovulation as the primary mode of action, on a stable dose for at least 28 days prior to screening visit;
- Intrauterine device (IUD) inserted at least 28 days prior to screening visit;
- Intrauterine hormone-releasing system;
- Partner vasectomized for at least three months prior to screening visit;

CONFIDENTIAL

Page 32 of 86

	
Title 43QM2106 Clinical Study Protocol – QM1114 – GL
	
Doc id MA-49290

--	--	-----------------------------------

Effective date: 2022-03-21 13:08

Effective

Version: 3.0

- Progestogen-only oral, injectable or implantable contraceptives that inhibit ovulation as the primary mode of action, on a stable dose for at least 28 days prior to screening visit; or
- Strict abstinence (i.e., refraining from heterosexual intercourse for the duration of the subject's participation in the study).

6. Time and ability to complete the study and comply with instructions.
7. Understands the study requirements and signed the informed consent form (ICF).

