9.1.5 Inferential Statistical Analyses

The primary efficacy endpoint will be a responder rate based on the subject GAIS at Month 1. A responder is defined as a subject who responds at least “Improved” on the GAIS at maximum frown. The null hypothesis of no relationship between treatment and responder rate will be tested against the alternative hypothesis that there is a relationship between treatment and responder rate. The responder rates of the QM1114-DP and placebo will be compared using a Cochran-Mantel-Haenszel test, stratified by site, at 5% significance level (2-sided) based on the ITT population. Missing Month 1 GAIS data will be imputed with ‘No Change’. For consistency across strata (site), the Breslow-Day test will be used to assess the homogeneity of the odds ratios across all sites. Depending on the number of sites, pooling of sites may be needed.

For the primary efficacy endpoint, consistency of the results will be analyzed using Cochran-Mantel-Haenszel test stratified by gender, baseline ILA, prior use of botulinum toxin, and Fitzpatrick skin type, respectively.

[figure not shown]
All other efficacy and safety endpoints will be analyzed descriptively as appropriate.

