9.2.2 Assumptions

CCI

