2.4.3 Primary analysis

The primary efficacy endpoint will be a responder rate based on the subject GAIS at maximum frown at Month 1 (described in [Section 1.4.1](#)). To evaluate the effectiveness and superiority in aesthetic improvement of QM1114-DP versus placebo in the treatment of moderate to severe GL, the responder rates of QM1114-DP and placebo will be compared using a Cochran-Mantel-Haenszel (CMH) test stratified by site at the 5% significance level (2-sided). The primary efficacy endpoint will be based on the ITT population where missing Month 1 GAIS data will be imputed with 'No Change'.

The null hypothesis of no relationship between treatment and responder rate (i.e., the responder rates are the same in both groups) will be tested against the alternative hypothesis that there is a relationship between treatment and responder rate (i.e., the responder rates are different in the two groups). For a significant result, the two-sided p-value of the comparison of the GAIS responder rate between the QM1114-DP and placebo subjects at Month 1 using the CMH test needs to be smaller than 0.05. For consistency across strata (site), the Breslow-Day test will be used to assess the homogeneity of odds ratios across all sites. If the Breslow-Day test is significant, then the responder rates between the QM1114-DP and Placebo treatment groups will be presented by site.

The estimates of the GAIS responder rates in each treatment group will be presented as well as the difference in responder rates (QM1114-DP responder rate – placebo responder rate). Corresponding 95% CI for the treatment group GAIS responder rates and the difference in responder rates along with the p-value for the difference will also be presented. The normal approximation (Wald) method will be used to calculate both the 95% CI for the individual treatment group GAIS responder rates and the 95% CI for the difference in responder rates. The above responder rates will be presented in figures by visit and treatment group.

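### The subgroup-stratified CMH test cannot show whether the treatment effect is consistent across subgroups, and no comparison between subgroup categories is planned

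*SAP*

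**What the plan says.** Protocol 9.1.5 states that, for the primary endpoint, "consistency of the results will be analyzed using Cochran-Mantel-Haenszel test stratified by gender, baseline ILA, prior use of botulinum toxin, and Fitzpatrick skin type", each in turn. SAP 2.4.4.2 gives the same purpose. It repeats the primary analysis of SAP 2.4.3 in the ITT population with No Change imputation, stratifying for each factor, and then adds: "The Breslow-Day test will not be used to assess the homogeneity of odds ratios across subgroup categories". No other interaction test or between-category contrast is named.

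The next sentence of SAP 2.4.4.2 plans responder rates, the treatment difference and its 95% CI for each subgroup. The interval method is not restated there, so the Wald method of SAP 2.4.3 carries over. For sites, by contrast, both documents do plan a Breslow-Day test of homogeneity.

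Prior toxin is split into five brand categories, with no rule for assigning a subject to one of them. Protocol 5.2.1 requires "Previous repeated treatments with BoNT-A products for aesthetic use within 3 years prior to the screening visit", and footnote 4 of the Schedule of Assessments has brand, area and date recorded for previous toxin treatments.

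**The concern.** The stated question is whether the effect is similar in men and women, in moderate and severe lines, and so on. The test named for it asks whether treatment and response are associated after adjusting for the factor. That is the primary question again with a different stratifier. With a large overall effect, one small discordant category hardly moves the answer.

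The risk lies in reporting. Four significant p-values could be presented under a consistency heading although they do not bear on consistency. For prior toxin there is a further gap: a CMH test needs each subject in exactly one stratum, and a subject with repeated treatments may have used more than one brand.

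**Working it through.** **The plan's own figures.** Protocol 5.1 anticipates 10% screen failure for 120 enrolled: 120 / 0.90 = 133.3, rounded up to 134, as stated. The sample size of 120 cannot be reproduced because protocol 9.2.1–9.2.3 is redacted.

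**Inputs.** From the documents: 90 vs 30 subjects, two-sided 5% level. Assumed: responder rates (redacted) and category sizes (not given). Each category is split 3:1.

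**Formula.** In category k, let a be the responders on QM1114-DP, n1 and n0 the group sizes, m the total responders and N = n1 + n0. Then E = n1·m/N, V = n1·n0·m·(N − m) / [N²(N − 1)], and CMH = (Σa − ΣE)² / ΣV on 1 df. Differences between observed and expected counts are summed before squaring, so a category pointing the other way is netted off and not flagged.

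**Example 1: a 20% category with a reversed effect.** Main category 58/72 vs 5/24; discordant category 3/18 vs 2/6.
- Main: E = 72·63/96 = 47.25, V = 4.103, a − E = 10.75.
- Discordant: E = 18·5/24 = 3.75, V = 0.774, a − E = −0.75.
- CMH = 10.00² / 4.878 = 20.5, p = 0.000006.
- Breslow-Day on the same data: p = 0.0004.
- Planned Wald output for the discordant category: −16.7 points (95% CI −58 to 25).
- Difference in risk differences, adding one success and one failure to each arm: main 59/74 − 6/26 = 0.567 (variance 0.0090); discordant 4/20 − 3/8 = −0.175 (variance 0.0373). Contrast 0.742, SE √0.0463 = 0.215, 95% CI 0.32 to 1.16.

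**Example 2: a reversed category of half the subjects.** 27/45 vs 3/15 and 9/45 vs 6/15. The a − E values are 4.5 and −2.25, and ΣV = 2.860 + 2.145 = 5.005. CMH = 2.25² / 5.005 = 1.01, p = 0.31; Breslow-Day p = 0.0025. Both examples are discordant, yet the CMH is significant in one and not in the other.

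**Simulation** (20,000 trials per scenario, two categories, CMH without continuity correction). Percentage of trials with CMH significant in favour of QM1114-DP, by share of subjects in the discordant category:

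| Rates elsewhere | Discordant category | 10% | 20% | 33% | 50% |
|---|---|---|---|---|---|
| 90% vs 10% | no effect | 100 | 100 | 100 | 99.9 |
| 80% vs 20% | no effect | 100 | 99.9 | 99.1 | 91.6 |
| 60% vs 20% | no effect | 95.6 | 91.0 | 80.2 | 57.6 |
| 50% vs 20% | no effect | 77.9 | 68.1 | 54.0 | 35.6 |
| 90% vs 10% | placebo 20 points higher | 100 | 100 | 100 | 94.5 |
| 80% vs 20% | placebo 20 points higher | 100 | 99.6 | 94.0 | 55.7 |
| 60% vs 20% | placebo 20 points higher | 92.9 | 80.2 | 51.4 | 16.7 |
| 50% vs 20% | placebo 20 points higher | 70.5 | 50.9 | 25.0 | 6.7 |

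For no-effect categories of 10–40%, the ranges are 100% at 95% vs 10%, 98–100% at 80% vs 20%, and 72–96% at 60% vs 20%.

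**What the planned intervals show.** The Wald interval of a no-effect category had a lower limit at or below 0 in 86–96% of runs. A 10% category, however, has about 9 vs 3 subjects. Suppose the true effect there is the same as elsewhere. Summing binomial probabilities over all 10 × 4 = 40 outcomes, Wald coverage is 53% at 95% vs 10% and 76% at 80% vs 20%. At 95% vs 10% the interval has zero width with probability (0.95⁹ + 0.05⁹)(0.9³ + 0.1³) = 0.630 × 0.730 = 0.46. Agresti-Caffo coverage by the same enumeration is 95% and 96%.

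**What an interaction contrast adds.** Tested at two-sided 5%, the Agresti-Caffo contrast detects a no-effect category of 10–40% in about 100% of trials at 95% vs 10%, 77–96% at 80% vs 20%, and 38–64% at 60% vs 20%. Its false-positive rate is 1.3–3.7%. For a category with half the effect (10–50% of subjects), power is about 25–41% at 80% vs 20% and 12–19% at 60% vs 20%.

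**The case against.** The strongest reply is that consistency will not be judged on the CMH p-value alone. Rates, differences and CIs by subgroup are planned, and a null or reversed category would normally be visible in them. That stands, and it keeps the point modest. Two gaps remain. An interval that includes 0 in a small category does not establish a difference from the other category, and the carried-over Wald intervals are least reliable in exactly those categories.

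A reader might infer that the plan will declare consistency whatever the truth. The documents do not support this. Neither section says that a significant subgroup-stratified CMH means consistent; the only p < 0.05 success rule is for the primary comparison. The test is also not always significant. With a reversed category (5% vs 40%) holding half the subjects, it is significant in about 86% of trials at 95% vs 10% elsewhere, 31% at 80% vs 20%, and 5% at 60% vs 20%. A reader might also infer that all heterogeneity testing is forbidden. Only Breslow-Day is excluded; the point is that nothing replaces it.

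The low power of interaction tests is a fair objection for modest differences, as the half-effect figures show, and for prior toxin, where five brands share 30 placebo subjects (30/5 = 6 on average). It argues for an exploratory estimate with its interval. It does not argue for a test of a different question.

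On brands, overlap is inferred from the eligibility criterion and not stated. Because brand and dates are recorded, an assignment rule can be derived. This is missing detail rather than an error.

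**Conclusion.** The point holds in limited form. The subgroup-stratified CMH tests the pooled, factor-adjusted effect and cannot support a claim of consistency, and no between-category comparison is planned. When the overall effect is large and the discordant category is a minority, the test is usually significant even if that category has no effect; the probability falls as the category grows, the effect elsewhere shrinks or the category's effect reverses. The planned descriptive output mitigates this but is imprecise in small categories. All sizes rest on assumed responder rates and category shares. The subgroup analysis is supportive, so the primary test, estimate and conclusion are unaffected. The change is worth making before unblinding, but it is not critical.

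**What to change.** In SAP 2.4.4.2:

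1. State that the subgroup-stratified CMH p-values are factor-adjusted repeats of the primary test and will not be used as evidence of consistency.
2. Base consistency on the planned differences by category, with Agresti-Caffo or Newcombe intervals in place of Wald, ideally in a forest plot.
3. For each factor, add the treatment-by-subgroup difference in risk differences with 95% CI, labelled exploratory. State that a non-significant result does not prove consistency.
4. Assign each subject to a single prior-toxin category by a rule fixed before unblinding, for example the most recent brand recorded.

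The cost is SAP wording and one table or figure, from data already collected. The downside is that the contrast is insensitive to modest differences and, for prior toxin, will be very imprecise.

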2.4.5 Secondary analysis

The secondary analysis will be based on the ITT population, using OC unless otherwise specified.

2.4.5.1 Secondary Efficacy Estimands

The estimands of the secondary endpoints can be written out in a similar manner as the estimand of the primary endpoint. Secondary endpoints share the following attributes of estimands:

Population: all randomized subjects (ITT population)	
Intercurrent Events: 
1. Missing observations for assessments2. Administered treatment not according to randomization3. Use of prohibited treatment in or near treatment area between 9 months prior to study treatment and prior to study end4. History or presence of eyelid or eyebrow ptosis at Baseline	
1. Use observed cases, leave response missing.2. Use observed response.3. Use observed response.4. Use observed response.

High-level descriptions of summary measures for the secondary efficacy endpoints are outlined below:

- Time to onset of treatment effect:
 - Endpoint: Onset of effect is defined as the first day a subject answers “yes” to the diary question.
 - Summary measure: descriptive statistics of time-to-event of subject responding “yes” to the diary question for QM1114-DP and placebo.
- GAIS responder rate:
 - Endpoint: Responder rate based on the 7-point GAIS where a responder is defined as a subject who responds at least “Improved” on the GAIS at maximum frown.
 - Summary measure: descriptive statistics of proportion of subjects that have at least “Improved” for QM1114-DP and placebo by visit.

[figure not shown]
CCI

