In the early 1990s, patients treated with BoNT-A for blepharospasm were observed to lose their frown lines and,^{5,9} since publishing these observations, the use of BoNT-A in the aesthetic setting has accelerated. Injectable BoNT-A products have been investigated for multiple aesthetic indications in attempts to reverse the appearance of aging, especially in the facial region.² In the treatment of facial lines, the effect of BoNT-A injections usually persists for approximately 4-6 months. Facial muscle activity and severity of the facial wrinkles then returns to baseline. Full functionality of facial muscles is usually restored by approximately 6 months post-treatment.¹⁰

There are four BoNT-A products currently licensed in the US for the treatment of GL in adults (Botox Cosmetic®, Dysport®, Xeomin®, and Jeuveau™). QM1114-DP is a novel botulinum toxin type-A1 which is presented as a liquid formulation. Unlike the main commercially available botulinum toxins in the United States (US), QM1114-DP is manufactured and formulated without any animal or human proteins. As a novel BoNT-A with a differentiated formulation, QM1114-DP is being developed for the treatment of moderate to severe GL in adults over 18 years.

 GALDERMA EST. 1981	Title 43QM2106 Clinical Study Protocol – QM1114 – GL	Doc id MA-49290
---	--	---------------------------

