2.1.2 Secondary Efficacy Objectives and Endpoints

The secondary efficacy objectives and endpoints of the study are:

[figure not shown]
1. To evaluate onset of treatment effect following a single dose of QM1114-DP and placebo as assessed by the subject using the diary card on Days 0 through 7 post-treatment.

Endpoint: Onset of effect is defined as the first day a subject answers “yes” to the diary question.

2. To evaluate aesthetic improvement following a single dose of QM1114-DP and placebo as assessed by the subject using the GAIS at maximum frown at all applicable time points.

Endpoint: Responder rate based on the 7-point GAIS. A responder is defined as a subject who responds at least “Improved” on the GAIS at maximum frown.

CCI

[figure not shown]

Effective date: 2022-03-21 13:08

Effective

Version: 3.0

CCI

 EST. 1981	Title 43QM2106 Clinical Study Protocol – QM1114 – GL	Doc id MA-49290
---	--	---------------------------

CCI

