5.4.5 Prohibited Concomitant Therapies

The following therapies are prohibited because they may interfere with the efficacy and/or safety assessment of the study products(s):

- Botulinum toxin of any serotype.
- Any other investigational new drug or device.

CONFIDENTIAL

Page 35 of 86

 EST. 1981	Title 43QM2106 Clinical Study Protocol – QM1114 – GL	Doc id MA-49290
---	--	---------------------------

- Any absorbable (temporary) or non-absorbable (permanent) material in the treatment area.
- Facial aesthetic procedures (e.g., ablative skin resurfacing, laser treatment, micro needling, photodynamic therapy, tattooing or chemical peel) or any other procedures in the treatment area.
- Facial surgery or eye surgery (including LASIK procedure).
- Medications that affect neuromuscular transmission such as curare-like depolarizing agents, lincosamides, polymyxins, anticholinesterases and aminoglycoside antibiotics.

If a prohibited therapy becomes a necessary treatment for best clinical interest of the subject or due to safety reason, the Medical Monitor (Section 11.9) should be notified, if time permits, to discuss possible alternatives prior to administration of a prohibited therapy.

If a subject receives a prohibited therapy during the clinical study, the Medical Monitor (Section 11.9) should be notified to discuss the subject's continuation in the clinical study.

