2.4.4 Primary Efficacy Estimand

The primary estimand is the treatment difference between QM1114-DP and placebo in proportion of subjects that have at least “Improved” from baseline; the number of subjects that select “Improved”, “Much Improved”, or “Very Much Improved” on the GAIS at Month 1, divided by the number of subjects that completed the GAIS at Month 1, in all randomized subjects (ITT population).:

Primary Endpoint	Estimand	
Responder rate in aesthetic improvement at Month 1 as assessed by the subject using the GAIS		Population: all randomized subjects (ITT population)
Endpoint: the number of subjects that select “Improved”, “Much Improved”, or “Very Much Improved” on the GAIS at Month 1, divided by the number of subjects that completed the GAIS at Month 1		
	Intercurrent Events: 
 1. Missing Month 1 observation 2. Administered treatment not according to randomization 3. Use of prohibited treatment/procedure in or near the treatment area between 9 months prior to study treatment and Month 1 after study treatment 4. History or presence of eyelid or eyebrow ptosis at Baseline 	Handling of intercurrent events: 
 1. Impute using the result of ‘No Change’ 2. Use observed response 3. Use observed response 4. Use observed response
Summary measure: treatment difference of QM1114-DP and placebo in proportion of subjects that have at least “Improved” from baseline.		

Note that intercurrent events is defined as events occurring after treatment initiation that affect either the interpretation or the existence of measurements associated with the clinical question of interest.

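### Late GAIS responder rates keep ratings made after off-study toxin or filler, so another product's effect can count as response to the single study dose

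*SAP*

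**What the plan says.** The second secondary objective (Protocol 2.1.2) reads "To evaluate aesthetic improvement following a single dose of QM1114-DP and placebo as assessed by the subject using the GAIS at maximum frown", at every applicable time point. Protocol 7.1.1 carries the GAIS through Month 12 and fixes its reference as the appearance just before the injection.

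SAP 2.4.5.1 sets the estimand attributes shared by the secondary endpoints. Its third intercurrent event is "Use of prohibited treatment in or near treatment area between 9 months prior to study treatment and prior to study end", and the handling is "3. Use observed response". Missing ratings stay missing (observed cases).

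The list in Protocol 5.4.5 includes "Botulinum toxin of any serotype", any filler material in the treatment area, and facial aesthetic procedures. The stated reason for the prohibition is possible interference with the efficacy or safety assessment. After such use the Medical Monitor is told and continuation is discussed; withdrawal is not automatic. Under Protocol 5.5 a subject who leaves is asked to complete the Month 12/early-termination procedures, which include the GAIS (Protocol 8.1.9).

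The primary estimand (SAP 2.4.4) keeps the observed response in the same way for a shorter window: "Use of prohibited treatment/procedure in or near the treatment area between 9 months prior to study treatment and Month 1 after study treatment".

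**The concern.** The GAIS asks how the lines look now compared with before the study injection. It cannot tell which product caused a change. If a subject takes a commercial toxin during follow-up and then rates Improved, the rating describes that product, but the table shows a response to the study dose.

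The follow-up is long enough for this to matter. Protocol 1.1 states: "In the treatment of facial lines, the effect of BoNT-A injections usually persists for approximately 4-6 months". Entry requires "Previous repeated treatments with BoNT-A products for aesthetic use within 3 years prior to the screening visit", a quarter of subjects receive placebo, and there is no further study treatment. The late-visit responder rates are where a reader will look to see how long one dose works, and they are the rates open to this misattribution.

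**Working it through.** **No plan figure to reproduce.** The documents give no rate of off-study treatment and no expected late responder rate. The arithmetic below shows sensitivity, not an expected size.

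**1. Can ratings after off-study use enter the table?** Yes. Protocol 5.4.5 allows continuation, the GAIS is scheduled at each later visit, and SAP 2.4.5.1 keeps the observed value. A subject who leaves may still be rated at the early-termination visit.

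**2. Does another readable rule remove them?** No. The per-protocol analysis serves the Month 1 primary endpoint only (SAP 2.3.2, 2.4.4.1). The optional re-analyses in SAP 2.4.2 are discretionary and concern missing data.

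**3. Which visits are exposed?** Those at Months 6 to 12: seven visits. The schedule defines a month as 4 weeks, so Month 6 is week 24 (168 days, about 5.5 calendar months). If the 4-6 months in Protocol 1.1 are calendar months, Month 6 is still inside that range. Month 7 is week 28 (196 days, about 6.4 calendar months), so the six visits from Month 7 on lie beyond it.

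**4. Effect on one arm.** Let p be the rate due to the study dose, u the share of the arm that is not responding and takes an off-study product, and r the share of those users who then rate at least Improved. All three are assumptions.

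Reported rate = p + u × r, so the rise is u × r, in percentage points:

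| r | u = 2% | u = 5% | u = 10% | u = 20% |
|---|---|---|---|---|
| 0.5 | 1.0 | 2.5 | 5.0 | 10.0 |
| 0.7 | 1.4 | 3.5 | 7.0 | 14.0 |
| 0.9 | 1.8 | 4.5 | 9.0 | 18.0 |

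Example, active arm, n = 90 (Protocol 9.2), p = 30%, u = 10%, r = 0.9: 0.30 + 0.10 × 0.9 = 39%. The Wald half-width is 1.96 × √(0.39 × 0.61 / 90) = 10.1 points, so the 9-point rise is about as large as the sampling error. It corresponds to 90 × 0.10 × 0.9 = 8.1 subjects.

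Placebo arm, n = 30: one such subject adds 1/30 = 3.3 points with all 30 in the denominator, and more if fewer are rated.

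**5. Effect on the contrast.** With p = 30% active and 5% placebo (25 points) and r = 0.9:

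| u, active | u, placebo | Active | Placebo | Difference |
|---|---|---|---|---|
| 10% | 10% | 39% | 14% | 25 |
| 10% | 20% | 39% | 23% | 16 |
| 20% | 10% | 48% | 14% | 34 |

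The difference can stay the same, shrink or grow.

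**The case against.** Keeping the observed response is a recognised treatment-policy strategy. The SAP names the event and its handling in advance, and off-study use remains visible because protocol deviations and concomitant procedures are summarised by arm and listed. That stands, but the SAP gives no reason for choosing this strategy for an objective about the effect of one dose.

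The frequency may be low. Exclusions 2 and 16 remove subjects who anticipate needing toxin or plan facial procedures, and the restrictions are explained at screening. Subjects who leave in order to be treated have no later ratings, apart from a possible early-termination visit. All of this stands and limits the likely size.

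Three stronger readings are tempting, and the documents do not support them:

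- *The late active-placebo difference is biased downward.* This needs more off-study use on placebo, which no section states. The secondary GAIS rates are descriptive and shown separately by arm (Protocol 9.1.5, SAP 2.4.5.3), and the readable text plans no late-visit difference.
- *The duration analysis is wrong.* Protocol 9.1.3 names Kaplan-Meier analysis of duration of response, but its definition is not readable. It may not use the GAIS, and it may have its own rule for off-study therapy.
- *The primary result is compromised.* Late use cannot affect Month 1. For use before Month 1, SAP 2.4.4.1 repeats the primary analysis in the per-protocol population to address deviations, and nothing in the documents suggests a material size there.

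**Conclusion.** The point holds for the secondary GAIS responder rates at the late visits. A non-responder who takes another product can only leave the arm's rate unchanged or raise it. The protocol itself expects such products to interfere with assessment, and no readable rule corrects for them.

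The size is unknown. Under the assumed ranges (u from 2% to 20%, r from 0.5 to 0.9) the rise is about 1 to 18 points per arm. The direction for a single arm is firm; the direction for the contrast is not. The confirmatory Month 1 test is not touched by late use. Redacted text could contain a further rule, which cannot be judged here.

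**What to change.** In SAP 2.4.5.1, split the third intercurrent event:

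- **Use before study treatment:** keep the observed response. Separating it also fits the SAP's own note in 2.4.4, which defines intercurrent events as arising after treatment starts, whereas this window opens 9 months earlier.
- **Use after baseline:** from the first botulinum toxin, filler or prohibited aesthetic procedure in or near the treatment area, count the subject as a GAIS non-responder at that visit and all later ones. Keep to the SAP's own area. Extending the rule to the whole face would turn a subject still responding in the glabella into a permanent non-responder because of treatment elsewhere. State whether visits missed after that date also count.

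Keep the observed-response table as supportive, and report the number and timing of such treatments by arm. Apply the same handling to duration of response only if its redacted definition has no such rule. Leave the Month 1 estimand unchanged.

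The cost is SAP wording, one derived flag and one extra table. Concomitant therapies are already reviewed at every visit (Protocol 5.4.3). One check is needed: treated area is specified for previous toxin (schedule footnote 4) and for fillers (Protocol 5.4.2), but not expressly for toxin taken on study, so confirm that the form records it. The downside is that late rates may be slightly understated for subjects who were still responding when they took another product; the supportive table shows by how much. The change concerns analysis only and alters no rule of subject management.
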